10.5 Urinalysis

- Phase I only: In cycle 1, urinalysis will be tested prior to each dose of hu3F8-BsAb and approximately one week after the second dose. (Pre-treatment urinalysis can be used for pre-cycle1 test.)
- **10.6** Liver and kidney function blood tests (ALT, AST, alkaline phosphatase, albumin, bilirubin, BUN and creatinine), and serum electrolytes (sodium, potassium, chloride, bicarbonate, magnesium, and phosphate).

- Phase I cycle 1: Before each dose of hu3F8-BsAb, within 72 hours after each dose of hu3F8-BsAb, and on approximately Day 15. (Pre-treatment test can be used for pre-cycle1 test.)
- For subsequent cycles in Phase I, and Phase II: Before each dose of hu3F8-BsAb. (Pre-treatment test can be used for pre-cycle1 test.)
- **10.7** Pregnancy test within 2 weeks before each cycle, if applicable.
- **10.8** Phase I only: Electrocardiogram will be done post the first infusion of hu3F8-BsAb on Day 1 and prior to the second dose hu3F8-BsAb on Day 8 during cycle 1. This must be done on the same day as the dose, but does not need to be immediately post or immediately prior.
- **10.9** Phase I only: Pharmacokinetic studies will be done as described in Section 9.1.4
- **10.10** Phase I and II: Cmax and Ctrough will be measured as described in Section 9.1.4
- **10.11** Ferritin and C-reactive protein
 - Phase I cycle 1: On Day 8 (prior to the second dose of hu3F8-BsAb) and approximately on Day 28.
 - For subsequent cycles in phase I, and phase II: If CRS is suspected based on clinical symptoms. (See Section 11.3)
- 10.12 LDH
 - Phase I cycle 1: On Day 8 (prior to the second dose of hu3F8-BsAb) and approximately on Day 28.
 - For subsequent cycles in phase I, and phase II: If CRS is suspected based on clinical symptoms. (See Section 11.3)
- **10.13** Blood will be obtained before each cycle of hu3F8-BsAb to assay for HAHA titers, then approximately every 3 months for 24 months from first hu3F8-BsAb dose, and then approximately every 6 months for up to 5 years from first hu3F8 dose or until patient is off study, whichever is earlier. This blood sample may also be tested for HAMA.
- **10.14** Blood will be tested for cytokine studies including IFN-y, IL-6, IL-8, IL-10.
 - Phase I cycle 1: cytokine studies should be tested prior to and ~ 6-8 hrs after the first and second infusion of hu3F8-BsAb, and on Days 2, 3, 4, 9, 10, and 11.
 - For subsequent cycles in Phase I and Phase II: If CRS is suspected based on clinical symptoms. (See Section 11.3)

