11 TOXICITIES/SIDE EFFECTS

- **11.1** Information regarding the definition and reporting of adverse events, including serious adverse events, is provided in Section 17.2.
- 11.2 Hu3F8-BsAb is expected to be associated with the known side effects of m3F8 and hu3F8

Common side effects: pain, paresthesia, hypertension, hypotension, sympathetic neuropathy, presyncope, syncope, tachycardia, urticaria, pruritus, flushing, fever, somnolence, nausea, and emesis.

Less common side effects: diarrhea, serum sickness, hyponatremia, airway constriction, peripheral neuropathy, impaired accommodation of the eye, poor reactivity of pupils to light, transaminitis.

Rare but serious side effects: anaphylaxis, posterior reversible encephalopathy syndrome (PRES)

11.3 Cytokine release syndrome (CRS) has been reported in patients with B cell leukemia or lymphoma treated by anti-CD19 T cell immunotherapies (e.g. blinatumomab, anti-CD19 CAR-modified T cells). CRS correlated with anti-tumor efficacy, and the incidence, severity, and onset of CRS depend on therapeutic agents, cancer type, tumor burden, and patient's immune system.^{64,65,67,79,86-89} Severe cytokine release syndrome is characterized by fever (\geq 3days), elevation of serum cytokines, and clinical toxicities (hypotension, hypoxia, neurological symptoms). In NB patients, 19 patients were treated by anti-GD2 CAR-modified T cells therapy in a phase I study and severe CRS was not observed.⁹⁰ In adults, severe CRS is characterized by hypotension, respiratory distress and cardiac changes including arrhythmias, acute coronary syndrome, and impaired LV function, and neurological symptoms such as seizures. Instead of grading CRS according to CTCAE 4.0, CRS will be graded using the CRS revised grading system by Lee et al.⁹¹ described below in Table 8.

Grade	Toxicity
Grade 1	Symptoms are not life-threatening and require symptomatic treatment only, e.g. fever, nausea, fatigue, headache, myalgias, malaise
Grade 2	Symptoms require and respond to moderate intervention Oxygen requirement < 40% or Hypotension responsive to fluids or low dose of one vasopressor or Grade 2 organ toxicity

Table 8CRS revised grading system91

[figure not shown]
Grade	Toxicity	
Grade 3	Symptoms require and respond to aggressive intervention	
	Oxygen requirement $\geq 40\%$ or	
	Hypotension requiring high dose for \geq 3 hours * or multiple vasopressors or	
	Grade 3 organ toxicity or Grade 4 transaminitis	
Grade 4	Life-threatening symptoms	

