2.1.3. Evaluation During Treatment/Intervention

The following evaluations will be performed during the treatment period.

Tests	Pre-treatment	During Treatment	During Follow-up
Complete history and physical	\checkmark	Cycle 1: Daily from Day 1 through Day 4, on Day 8, then weekly thereafter until Day 28 Subsequent Cycles: Before each dose of hu3F8-	-
Pharmacokinetic studies (research blood)	√	See Protocol Section 9.1 Cycle 1: See PK Section 6.8 Subsequent Cycles: Before each dose of hu3F8- BsAb, ~5 minutes after hu3F8-BsAb infusion	
Complete Blood Count	~	Cycle 1: Approximately Days 2, 5, 8 (prior to the second dose of hu3F8- BsAb), and approximately Days 15 and 28. Subsequent Cycles: Before each dose of hu3F8-BsAb	-
Liver and Renal function tests (ALT, AST, alkaline phosphatase, albumin, bilirubin, BUN and creatinine) and serum electrolytes (sodium, potassium, chloride, bicarbonate, magnesium, and phosphate)	✓	Cycle 1: Before each dose of hu3F8- BsAb, within 72 hours after each dose of hu3F8-BsAb and approximately Day 15 Subsequent Cycles: Before each dose of hu3F8-BsAb	-
C3 & CH50	~	Cycle 1 Only: Day 2	-
Lactate dehydrogenase (LDH)	~	Cycle 1: Day 8 and approximately Day 28 Subsequent Cycles: If CRS is suspected based on clinical symptoms	
Ferritin and C-reactive protein (CRP)	\checkmark	Cycle 1: Day 8 and approximately Day 28 Subsequent Cycles: If CRS is suspected based on clinical symptoms	-
Pulse Oxymeter (SpO2) and Blood pressure measurement	Blood pressure (BP) measurement (standing, sitting, lying down)	SpO2: During hu3F8-BsAb infusion BP: No later than 30 minutes after the end of hu3F8-BsAb infusion Cycle 1: Blood pressure measurement (standing, sitting, lying down) pre infusion, once daily throughout hospital stay and at discharge. For outpatient treatment: pre infusion and at discharge	-
Blood for HAHA	~	Before each cycle	Approximately q3 months for 24 months from first hu3F8-BsAb dose and then q6 months for up to 5 years from first dose or until patient is off trial, whichever is earlier
Urinalysis	~	Cycle 1: Prior to each dose of hu3F8-BsAb and approximately one week after the second dose	-
Pregnancy test, if applicable	✓	Within 2 weeks before each cycle	-
Electrocardiogram (ECG)	✓	Cycle 1: Post-infusion of the first dose and prior to the second dose on Day 8	-

Table 2 Phase I - Evaluation During Treatment/Intervention

Echocardiogram (ECHO)	\checkmark	-	-

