Cytokine studies (research blood)	~	Cycle 1: prior to and ~ 6-8 hrs after the first and second hu3F8-BsAb dose, and on Days 2, 3, 4, 9, 10 and 11 Subsequent Cycles: If CRS is suspected based on clinical symptoms	-
Lymphocyte subsets, T cell activation/exhaustion markers (research blood)	*	Cycle 1: on Days 2, 8 (prior to hu3F8-BsAb), 9, 10, and 11, and approximately on Days 15 and 28 Subsequent Cycles: Before each dose of hu3F8-BsAb	-
Bone Marrow (BM) studies*	\checkmark	Any time after the second dose in cycle 2 and cycle 4 and approximately every 3 months thereafter	-
Computed Tomography (CT) / Magnetic Resonance Imaging (MRI), Metaiodobenzyl- guanidine (MIBG) scan* with/without Positron Emission Tomography (PET), bone scan	~	Any time after the second dose in cycle 2 and cycle 4 and approximately every 3 months thereafter	-
Pain Assessment	~	On days of hu3F8-BsAb treatment: prior to hu3F8-BsAb administration, during acute pain episode, and ~1 hour after the end of infusion or prior to discharge from the PDH	-
Stool Microbiome	✓ , where feasible	-	-

* Only for NB patients

Tests	Pre-treatment	During Treatment	During Follow-up
Complete history and physical	✓	Before each dose of hu3F8-BsAb and within 72 hours of treatment	-
Complete Blood Count	✓	Before each dose of hu3F8-BsAb	-
Liver and Renal function tests (ALT, AST, alkaline phosphatase, albumin, bilirubin, BUN and creatinine) and serum electrolytes (sodium, potassium, chloride, bicarbonate, magnesium, and phosphate)	1	Before each dose of hu3F8-BsAb	-
LDH	✓	If CRS is suspected based on clinical symptoms	
Ferritin and CRP	\checkmark	If CRS is suspected based on clinical symptoms	-
SpO2 and Blood pressure measurement	Blood pressure measurement (standing, sitting, lying down)	SpO2: During hu3F8-BsAb infusion BP: No later than 30 minutes after the end of hu3F8-BsAb infusion Cycle 1: Blood pressure measurement (standing, sitting, lying down) pre infusion, once daily throughout hospital stay and at discharge. For outpatient treatment: pre infusion and at discharge	-
Blood for HAHA	✓ (If applicable)	Before each cycle	Approximately q3 months for 24 months and then q6 months for up to 5 years from first hu3F8 dose or until patient is off trial, whichever is earlier
Urinalysis	✓	Cycle 1: Prior to each dose of hu3F8-BsAb and approximately one week after the second dose	-
Pregnancy test, if applicable	✓	Within 2 weeks before each cycle	-
ECG	✓	-	-
ЕСНО	✓	-	-

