6.6.6.3. Immunological effects of hu3F8-BsAb for Phases I and II

Biologic correlate studies include (1) host immunity, (2) host T cell cytotoxic capacity, and (3) T cell homing into the tumor.

The parameters measured for each patient under "host immunity" include:

- the induction of HAHA,
- the induction of Ab3,
- the induction of Ab3'.

Under "T cell cytotoxic capacity", the following measurements will be made:

- (1) cytokine profiles including IFN-y, IL-6, IL-8, IL-10,

- (2) changes in lymphocyte populations and their differentiation including CD3, CD4, CD8, Foxp3, CD127, CD45RA, CCR7, and
- (3) activation and exhaustion markers on T cells including CD25 and PD-1.

"T cell homing" will be tested by immunohistochemistry of tumor samples if available.

For phase I, spaghetti plots of available data will be performed based on patients from the Safety Analysis Set.

For phase II, available data will be described by dose group (Neuroblastoma vs Osteosarcoma) based on patients from the Safety Analysis Set.

Available data will be also presented in a data listing.

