For analysis purposes, values preceded by a "<" (i.e. those below the limits of quantification) will be considered equal to the half of the Lower Limit Of The Quantification (LLOQ/2). Those preceded by a ">" sign (i.e. those above the limits of quantification) will be considered equal to the upper limit of quantification.

Laboratory values will be assigned toxicity grades, when available*, using criteria based on the NCI CTCAE version 4.03^9 .

Parameters whose grade can be derived are the followings:

- Hematology
 - Hemoglobin (Low)
 - Hemoglobin (High)
 - WBC (Low)
 - WBC (High)
 - Neutrophils (absolute) (Low)
 - Lymphocytes (absolute) (Low)
 - Lymphocytes (absolute) (High)
 - Platelet (Low)
- Serum chemistry
 - \circ Sodium (Low)
 - Sodium (High)
 - o Potassium (Low)
 - Potassium (High)
 - Magnesium (Low)
 - Magnesium (High)
 - Creatinine (High)
 - Total Bilirubin (High)
 - ALT (High)
 - AST (High)
 - ALP (High)
 - Albumin (Low)

Laboratory data will be summarized by default descriptive summary statistics for continuous and categorical variables for the Safety Analysis Set by treatment group and overall as follows:

- Observed values and absolute change from baseline at each assessed timepoint for each standard continuous laboratory parameter;
- Number and percentage of patients with categorized shift (low, normal and high) values relative to the reference range at baseline compared to each post-baseline value for hematology and serum chemistry (for phase II only);
- Number and percentage of patients with worst NCI-CTCAE toxicity values;
- Number and percentage of patients with categorized shift NCI-CTCAE toxicity values at baseline compared to worst post-baseline timepoint.

Listings of all clinical laboratory data including derived percentage change from baseline will be provided for the Safety Analysis Set. Within each listing, laboratory values outside the

normal ranges will be flagged as either high or low and NCI-CTCAE grading will be provided for applicable laboratory assessments.

In addition, the following figures will be displayed:

- Longitudinal plot of laboratory parameters in patient with at least one abnormal value (Three different plot symbols will indicate whether the values were Low, Normal or High)
- Baseline and post baseline plot of laboratory parameters per cycle and per week

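### After Phase I Cycle 1, ferritin, CRP and LDH are drawn only when CRS is suspected, yet SAP 6.7.4 summarises them as ordinary chemistry

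*SAP*

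**What the plan says.** **Sampling.** Protocol 10.11 (ferritin and CRP) and 10.12 (LDH) set one rule. In the opening cycle of Phase I everyone is sampled: "Phase I cycle 1: On Day 8 (prior to the second dose of hu3F8-BsAb) and approximately on Day 28". After that the rule is "For subsequent cycles in phase I, and phase II: If CRS is suspected based on clinical symptoms". SAP Table 2 repeats this for Phase I: "Cycle 1: Day 8 and approximately Day 28 Subsequent Cycles: If CRS is suspected based on clinical symptoms". SAP Table 3, for Phase II, has a pre-treatment tick for these markers, and its only on-treatment entry is "If CRS is suspected based on clinical symptoms".

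**Analysis.** SAP 6.7.4, Table 7, lists ferritin, CRP and LDH under serum chemistry. For laboratory parameters that section plans "Observed values and absolute change from baseline at each assessed timepoint for each standard continuous laboratory parameter", a Phase II shift table against the reference range covering serum chemistry, and figures that include "Baseline and post baseline plot of laboratory parameters per cycle and per week". SAP 6.1 computes summary statistics for patients with data, and takes percentages over non-missing values unless a missing category is shown. SAP 5.2.2 does not impute laboratory data. SAP 5.1.4 uses nominal visits, with windows for scans only.

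**Cytokines** follow the same trigger (Protocol 9.4 and 10.14) but are analysed elsewhere. SAP 6.6.6.3 plans Phase I spaghetti plots, a listing, and this: "For phase II, available data will be described by dose group (Neuroblastoma vs Osteosarcoma".

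**The concern.** A by-timepoint mean is normally read as the state of the treated group at that time. Here the patients behind the mean change from everyone to those whose symptoms raised suspicion of a syndrome that these markers are used to work up. The Phase II shift table is the most exposed display, because every protocol-planned on-treatment value of these three markers in Phase II is a triggered one. Without a missing category, its percentage of high values would be taken over suspected cases alone.

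What is at stake is interpretation. Laboratory tables are presented by dose group in Phase I and by tumour group in Phase II. SAP 6.7.8.2 has the Phase I safety analyses prepared so that the DMC can recommend the MTD and RP2D, and SAP 6.7.2 says that safety data other than DLTs may bear on the final MTD. A selection artefact could be read there as a dose or cycle effect.

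**Working it through.** The plan states no figure on this point, so there is none to reproduce. The check sets the schedule against the displays and then illustrates direction and size under assumptions.

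**1. Who supplies a planned value**

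| Period | Ferritin, CRP, LDH |
|---|---|
| Baseline, both phases | all patients |
| Phase I Cycle 1 | all patients, Day 8 before dose 2 and about Day 28 |
| Phase I later cycles | suspected CRS only |
| Phase II, all on-treatment times | suspected CRS only |

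The scheduled Cycle 1 draws come about 7 days after dose 1 and about 20 days after dose 2 (28 − 8). Triggered draws come with symptoms. Cycle 1 and later cycles therefore differ in the timing of the draw as well as in who is sampled.

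**2. Whether the SAP separates the two kinds of value.** It does not. The reference in 6.7.4 to scheduled visits points to Tables 2 and 3, whose Phase II on-treatment entry is the trigger itself. The nominal-visit rule does not exclude triggered draws and does not say which timepoint they belong to.

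**3. Direction and size (assumed values).** Let the log-scale change have SD 1, with a mean shift of D when CRS is present. Let the CRS rate in a cycle be p, and let suspicion have sensitivity s and specificity c. There is no drift over time. Then:

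- mean in all patients = D × p
- share sampled = p·s + (1 − p)(1 − c)
- mean among those sampled = D × p·s / [p·s + (1 − p)(1 − c)]

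With p = 0.20, D = 1 and s = c = 0.9, the all-patient mean is 0.20. The share sampled is 0.18 + 0.08 = 0.26, and the sampled mean is 0.18/0.26 = 0.69. The overstatement is 0.49 SD.

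The scenarios cover p from 0.05 to 0.80, D of 1 or 2, and s/c of 0.9/0.9 or 0.8/0.7. The triggered mean exceeds the all-patient mean in all of them.
- Smallest excess, at p = 0.05, D = 1, 0.8/0.7: 0.04/0.325 − 0.05 = 0.07.
- Largest excess, at p = 0.30, D = 2, 0.9/0.9: 2 × (0.27/0.34 − 0.30) = 0.99.

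**4. Pattern over cycles 1 to 4** (D = 1; simulated with 200,000 patients per cycle)

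| CRS rate by cycle | s/c | Phase I observed means | Phase II observed means |
|---|---|---|---|
| 20% throughout | 0.9/0.9 | 0.20, 0.69, 0.69, 0.70 | 0.70, 0.69, 0.69, 0.69 |
| 50, 20, 10, 5% | 0.9/0.9 | 0.50, 0.69, 0.50, 0.33 | 0.90, 0.69, 0.50, 0.32 |
| 50, 20, 10, 5% | 0.8/0.7 | 0.50, 0.40, 0.23, 0.12 | 0.73, 0.40, 0.23, 0.13 |
| 80, 30, 20, 10% | 0.9/0.9 | 0.80, 0.79, 0.68, 0.50 | 0.98, 0.79, 0.69, 0.51 |

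Phase I can show one upward step after Cycle 1. A falling CRS rate can cancel or reverse it. Phase II is too high in level, with no built-in trend.

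**5. Group comparison.** Take two groups with the same p = 0.20 and D = 1, so both true means are 0.20. If CRS is suspected with 0.9/0.9 in one and 0.8/0.7 in the other, the displayed means are 0.69 and 0.16/0.40 = 0.40. The apparent difference is 0.29 where the true difference is zero.

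**6. Numbers behind a mean.** If 5% to 40% of patients are sampled in a cycle, a triggered summary rests on 1.5 to 12 of 30 patients (Phase I or Group 1) or 0.9 to 7.2 of 18 (Group 2), before attrition.

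**The case against.** The best defence is that these are descriptive displays, that the default statistics show n, and that table formats are left to shells which are not part of the documents. A small n would be visible, and the shells might keep triggered draws out of the by-visit means. This limits the stakes but does not remove the defect. A visible n does not tell the reader that the sample was selected on symptoms, and nothing in the SAP text tells the programmer to set these values apart.

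Three stronger readings are tempting and fail:

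- *The summaries rise with time on drug by construction.* A reader might infer this from the change in sampling. Steps 3 and 4 show bias in level, at most one step in Phase I, and declining means when CRS becomes rarer.
- *The same fault runs through the cytokine analysis.* Cytokines are not in Table 7, so the 6.7.4 summaries do not cover them. Spaghetti plots show each patient's own values and average nothing, and Phase I Cycle 1 cytokines are already sampled around the infusions. What remains is the unlabelled Phase II description by tumour group.
- *Selection on CRS is selection on efficacy.* Protocol 11.3 does say "CRS correlated with anti-tumor efficacy", but in the setting of anti-CD19 therapy for B-cell disease. The same section reports no severe CRS in 19 neuroblastoma patients given anti-GD2 CAR T cells. Protocol 14.3.2 plans to relate these markers to response, but SAP 6.6.6.3 specifies no such test.

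**Conclusion.** The concern holds for ferritin, CRP and LDH. As written, SAP 6.7.4 gives CRS-selected summaries for Phase I Cycle 2 onwards and for all of on-treatment Phase II. They will tend to overstate the level in all treated patients, and they mix differences between dose or tumour groups with differences in how often CRS is suspected.

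The direction rests on the markers being higher in CRS and on suspicion picking out CRS better than chance. The size cannot be derived from the documents, which give no CRS rate, marker SD or accuracy of suspicion; the range of 0.07 to 0.99 SD is illustrative. The statement covers protocol-planned draws, and additional local draws entered in the eCRF could dilute the selection.

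The reach is limited. No primary endpoint, secondary efficacy endpoint or DLT rule uses these values, and the three markers are not among the parameters that 6.7.4 grades by CTCAE. This is an inexpensive improvement to safety tables, some of which go to the DMC at the end of Phase I.

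**What to change.** In SAP 6.7.4:

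- Restrict by-timepoint change-from-baseline summaries and per-cycle mean plots of ferritin, CRP and LDH to baseline and the scheduled Phase I Cycle 1 timepoints.
- Leave these three out of the Phase II reference-range shift table.
- Summarise CRS-triggered values separately by CRS episode, giving the number sampled over the number treated in that cycle. This also settles which timepoint a triggered draw belongs to.

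In SAP 6.6.6.3:

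- Label Phase II and Cycle 2+ cytokine data as CRS-triggered, with the same denominator, and do not present them as a comparison between tumour groups.
- Individual Phase I spaghetti plots may keep triggered values if these are flagged.

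A related repair: Protocol Section 8 does not list LDH among the pre-treatment tests, while Protocol Tables 6 and 7 tick it. These should be reconciled, since LDH change from baseline needs that value.

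The cost is SAP wording and table shells, with no new data. The downside is fewer markers in the standard Phase II laboratory tables.

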6.7.5. Vital Signs

The analyses described below will be conducted for the following vital signs assessments respectively:

- SBP (mmHg);
- DBP (mmHg);
- Heart Rate (HR) (bpm);
- Pulse Oximeter at rest (%);
- Pulse Oximeter at exertion (%);

In accordance with the baseline value definition in Section 5.1.2, the absolute and percentage change from baseline will be derived as follows:

Absolute change (unit) = (post-baseline value – baseline value)

Percentage change from baseline = [(post-baseline value – baseline value) / baseline value] \times 100

The following will be summarized by treatment group (phase I) and cancer type (phase II) and overall for the Safety Analysis Set:

• Observed values and absolute change from baseline at each assessed timepoint for each standard vital sign parameter using default summary statistics for continuous variables

A listing of all vital signs data including derived percentage change from baseline will be provided for the Safety Analysis Set.

In addition, the following figures will be displayed:

- Longitudinal plot of vital signs parameters in patient with at least one abnormal value
- Baseline and post baseline plot of vital signs parameters per cycle and per week
- Scatter plot of vital signs parameters per cycle and per week

